6.4.2.7. Pulse Oximetry (Oxygen Saturation)

Oxygen (O₂) saturation will be measured by pulse oximetry at screening and repeated as clinically indicated throughout the study.

6.4.2.8. Neurological Assessment

A basic neurological exam (including, but not limited to, cranial nerve examination, motor function, sensory function, reflexes and cerebellar function) will be conducted as part of the physical examination.

6.4.2.9. Pregnancy Testing and Pregnancy Risk Counseling

Medically supervised (ie, performed in a clinic) serum or urine pregnancy tests with a sensitivity of at least 25 mIU/mL must be conducted in FCCBP/FCBP, including those who commit to complete abstinence. Female children of childbearing potential is defined as a female who has achieved menarche and/or breast development in Tanner Stage 2 or greater and has not undergone a hysterectomy (the surgical removal of the uterus) or bilateral oophorectomy (the surgical removal of both ovaries).

A female of childbearing potential is defined as a female who has achieved menarche at some point, not undergone a hysterectomy or bilateral oophorectomy and has not been naturally postmenopausal for at least 24 consecutive months (ie, has had menses at any time in the preceding 24 consecutive months).

For all applicable subjects during the Screening Period, 2 pregnancy tests (with sensitivity of at least 25 mIU/mL) must be conducted prior to starting treatment. The first pregnancy test in both FCCBP and FCBP must be performed within 10 to 14 days prior to the start of treatment (Screening Period) and the second pregnancy test must be performed within 24 hours prior to the start of treatment (Cycle 1, Day 1). Amenorrhea following cancer therapy does not rule out childbearing potential.

Note: The pregnancy test 10 to 14 days prior to initiation of pomalidomide may be omitted, at the discretion of the investigator, for any FCCBP/FCBP who has high acuity disease requiring immediate treatment with pomalidomide. The pregnancy test within 24 hours prior to the first dose of pomalidomide is required to be performed.

Female children of childbearing potential and FCCBP with regular or no menstrual cycles must agree to have subsequent pregnancy tests weekly for the first 28 days of study participation and then every 28 days while on study, at End of Treatment Visit and at day 28 following treatment discontinuation. If menstrual cycles are irregular, the pregnancy testing must occur weekly for the first 28 days and then every 14 days while on study, at study End of Treatment Visit, and at Days 14 and 28 following treatment discontinuation. It is the responsibility of the Investigator to obtain and review pregnancy test results for subject safety, and follow up with subjects in a timely manner.

The subject must not receive pomalidomide until the Investigator has verified that the results of the pregnancy test performed are negative. See inclusion criteria (Section 4.2) for pregnancy testing requirements.

The Investigator must confirm the FCCBP/FCBP subject is continuing to use 2 reliable methods of birth control if not committing to complete abstinence or plans not to commit to complete abstinence. Counseling about pregnancy precautions and the potential risks of fetal exposure to pomalidomide must be conducted at screening, on Day 1 (within 24 hours prior to treatment) of each cycle prior to pomalidomide dispensing or at a minimum of every 28 days (can also be conducted verbally from the site), at the End of Treatment Visit, and at the 28-day post-treatment Safety Follow-up Visit. If pregnancy or a positive pregnancy test does occur in a study subject, treatment must be immediately discontinued. Pregnancy testing and counseling must be performed if a subject misses her period or if her pregnancy test or her menstrual bleeding is abnormal. Treatment must be discontinued during this evaluation as well. Female children and adult females must agree to abstain from breastfeeding during study participation and for at least 28 days after treatment discontinuation. If pregnancy or a positive pregnancy test does occur in the partner of a male study subject during study participation, the Investigator must be notified immediately.

Furthermore, FCCBP/FCBP and male subjects that have reached puberty must agree to undergo physician-approved reproductive education and discuss the side effects of pomalidomide on reproduction with parent(s) and/or guardian(s) when appropriate. Pregnancy testing is not required for non-FCCBP subjects, unless deemed necessary by the Investigator.

Any pregnancy occurring in either a female subject or partner of a male subject while in the Treatment Period, or within 28 days thereafter, are considered immediately reportable events (see Section 10.4).

6.4.2.10. Assessment of Second Primary Malignancy

Second primary malignancies will be monitored as events of interest and must be reported as SAEs. This includes any SPM, regardless of causal relationship to treatment, occurring at any time for the duration of the study, for at least 5 years from enrollment of the last subject, unless consent/assent is withdrawn, the subject is lost to follow-up, or death. Subjects that do not receive treatment (eg, screen failures) will not be followed for SPM.

Events of SPM are to be reported using the SAE report form and must be considered an “Important Medical Event” if no other serious criteria apply; these events must also be documented in the appropriate page(s) of the eCRF (ie, AE and SPM eCRF) and subject’s source

documents. Documentation on the diagnosis of the SPM must be provided at the time of reporting as a SAE (eg, any confirmatory histology or cytology results, X-rays, CT scans, etc).

6.5. Pharmacokinetics – Optional

Sparse whole blood samples for PK analysis will be collected from consenting subjects at the time points specified in Table 6. Blood samples MUST be drawn from the arm contra lateral to the arm with the intravenous infusion of concomitant medications (if applicable). For each PK sample, draw approximately 1 mL blood and prepare plasma by centrifugation at 4°C. The dose of pomalidomide (Cycle 1: Day 8 and 15) should be administered to subjects in the morning after the collection of the pre-dose PK blood samples. To reduce PK variability on PK sampling days, subjects will be asked not to eat for 2 hours prior and 2 hours after pomalidomide administration. Specific details regarding the collection, processing, storage, and shipment of PK samples are provided in Appendix E.

Note: Blood samples for PK analysis can be obtained through a central line, if applicable. The use of the central line to collect PK samples and any concomitant medications given via the central line prior to sampling must be captured in the appropriate section of the subject’s eCRF and source documents.

Table 6: Pharmacokinetic Sampling Time Points

Collection Time Relative to Pomalidomide Administration	Collection Window	Cycle 1, Day 8	Cycle 1, Day 15
0 hour (pre-dose)	-90 min	x	x
2 hours	± 30 min	x	x

The following information must be captured on the PK visit days:

- Actual date and time for PK blood collections
- Administered dose of pomalidomide
- Actual date and time of pomalidomide oral administration

7. DESCRIPTION OF STUDY TREATMENTS

7.1. Description of Investigational Product

Investigational product will be provided as capsule formulation and oral suspension.

Pomalidomide oral capsules for this clinical study will be supplied by Celgene Corporation in 0.5 mg gelatin capsules (size 4 reddish brown), 1 mg hard gelatin capsules (size 4 reddish brown) and 2 mg, 3 mg and 4 mg hard gelatin capsules (size 2 reddish brown) labeled appropriately as IP for this study. Each bottle contains 21 capsules with each capsule containing pomalidomide as the active ingredient and the following inactive ingredients: mannitol, pre-gelatinized starch and sodium stearyl fumarate. The capsules are supplied in tamper-evident, child-resistant, opaque, high density polyethylene (HDPE bottles) with polypropylene caps.

Celgene Corporation will also supply pomalidomide active pharmaceutical ingredient in individually sealed vials for constitution to an oral suspension. Each vial contains 20 mg of pomalidomide, mannitol, pre-gelatinized starch and sodium stearyl fumarate. The pomalidomide powder in each vial is constituted with 4 ml of water and 5 ml of suspending agent to create a pomalidomide oral suspension with a final volume of 10 mL and a concentration of 2 mg/ml. This suspension is intended for oral administration only.

Please refer to the pomalidomide study drug label for more details on preparation, storage conditions, approved indications, known precautions, warnings and adverse reactions. Additional information may be included on the label as needed or applicable. Label(s) for study drug will contain information as required per local health authority. The pomalidomide dispensing, administration, dosing schedule and dose adjustments to be followed for this study are described in Section 7.2.

7.2. Treatment Administration and Schedule

The starting dose of pomalidomide will be 2.6 mg/m²/day, based on the subject's actual BSA calculated at the beginning of each cycle. Pomalidomide (oral capsules or suspension) will be administered daily for the first 21 days of every 28-day cycle and only enough pomalidomide for 1 cycle (21-day supply) of treatment will be dispensed on Day 1 of each new cycle of therapy. The oral suspension is available for use in subjects who are unable to swallow the capsules or at the discretion of the Investigator. On Day 1 of each cycle, pomalidomide will be dispensed and administered after completion of all clinical procedures required for that day. Subsequent pomalidomide administration (ie, Days 2-21 of each cycle) may occur at the subject's home.

Pomalidomide will not be administered on Days 22 through 28 of the 28-Day treatment cycle even if a subject experiences a toxicity that requires dose interruption (see Section 7.2.2). Counting of days should continue uninterrupted and the rest period (Days 22 to 28) should be continued as planned. For example, if a subject experiences a toxicity that requires interruption and does not recover until Day 22, pomalidomide should be restarted on Day 1 of the subsequent cycle if other protocol parameters are met. Subjects will continue treatment for up to 24 cycles or until documented PD, withdrawal of consent/assent, treatment becomes intolerable or death, whichever comes first.

For subjects receiving capsules, the pomalidomide dose should be calculated and rounded up or down to the nearest 0.5 mg as the prescribed dose before each new dosing cycle. The dose

prescribed should be based on the subject's BSA and yield the minimum number of capsules to achieve the prescribed dose. However, if a subject is unable to swallow larger capsules, varying appropriate strength combinations may be considered during medication assignment.

Pomalidomide capsules should not be broken, chewed or opened and should be taken at approximately the same time every day for 21 consecutive days in a cycle. If a dose is vomited within 15 minutes of taking the dose and the capsule(s) are visible in the emesis, the dose should be repeated and the Investigator should be notified to have replacement capsule(s) provided. If vomiting occurs beyond 15 minutes of dosing, do not repeat the dose and that day's dose should be skipped. Any vomiting of the capsules should be described in the subject dosing diary.

For subjects receiving the oral suspension of pomalidomide, the dose administered should correspond with a volume that is a 0.1 mL increment. The oral suspension should be taken at approximately the same time every day for 21 consecutive days in a cycle. If the dose is vomited, the dose should not be repeated for that dosing day and details entered in the subject dosing diary. If a subject is receiving the pomalidomide oral suspension, a home healthcare company can be available to assist with the preparation and administration of the oral suspension at the subject's home. The home trial support agent that may visit the subject's home would be a licensed nurse. Refer to the Pomalyst Oral Suspension Preparation Administration and Handling Guide for additional guidance.

Pomalidomide (capsules or oral suspension) can be taken with or without food or beverage; however, to reduce PK variability on PK sampling days in Cycle 1 (Days 8 and 15), consenting subjects should not eat for 2 hours prior and 2 hours after pomalidomide administration. A pomalidomide dosing table is provided in [Appendix F](#) to facilitate dosing calculation for both capsules and oral suspension. If a dose is forgotten but remembered within 8 hours, the missed dose should be taken/given immediately. If more than 8 hours have passed since the time the dose was due, that day's dose should be skipped.

Treatment administration will be accurately recorded including, but not limited to, date of administration, dose and any changes in dosage administration (eg, interruption or reduction in dosing due to an AE).

Females of childbearing potential should not handle or administer pomalidomide unless they are wearing gloves. All subjects should not extensively handle the pomalidomide capsule formulation or oral suspension and should maintain storage in the packaging until ingestion. In investigational studies, pomalidomide will be dispensed through a qualified healthcare professional (including but not limited to, nurses, pharmacists and physicians). These healthcare professionals will be trained by Celgene in requirements specific to counseling of subjects. Once trained, these healthcare staff will counsel subjects prior to pomalidomide being dispensed to ensure that the subject has complied with all requirements (including use of birth control and pregnancy testing) and that the subject understands the risks associated with pomalidomide. This step will be documented with a completed Education and Counseling Guidance Document and no pomalidomide will be dispensed until this step occurs. Counseling includes verification with the subject that required pregnancy testing was performed and results were negative.

A Pomalidomide Information Sheet will be supplied each time pomalidomide is dispensed.

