7.2.2. Dose Reductions, Interruptions and Discontinuation Criteria for Toxicities

Hematological and non-hematological toxicity will be graded using CTCAE version 4.03. In all cases, the reason for dose modification/interruption/discontinuation must be recorded in the subject's medical record. If the subject discontinues the protocol-prescribed therapy due to an AE, this event must be reported in accordance with the procedures outlined in Section 10.

Subjects who experience significant toxicity as listed below (Table 8) will have pomalidomide interrupted or reduced as specified in Table 7. Up to two dose reductions of pomalidomide are allowed across the Treatment Period in the event of specific protocol defined toxicity with no evidence of disease progression.

In addition:

- If a subject experiences a toxicity that requires interruption and does not recover until Day 22, pomalidomide (dose-reduced) should be restarted on Day 1 of the subsequent cycle if other protocol parameters are met.
- The dose will not be re-escalated following a dose reduction, even if there is minimal or no toxicity with the subsequent reduction in dose.
- Subjects who again experience dose modifying toxicity after 2 dose reductions will be taken off pomalidomide therapy.

- Subjects who experience hematologic toxicity (eg, neutropenia or thrombocytopenia) should have appropriate laboratory testing at least twice weekly (3 to 4 days apart) until the toxicity has resolved.
- If there is a > 14-day delay in starting the subsequent cycle for a pomalidomide-related toxicity, the investigator should consider pomalidomide dose reduction or pomalidomide discontinuation, based upon clinical judgment and the required dose modification criteria outlined in [Table 8](#).

Table 7: Dose Reductions of Pomalidomide

Dose Level	Dose
Starting dose	2.6 mg/m ² /day
Dose Level -1	1.9 mg/m ² /day
Dose Level -2	1.3 mg/m ² /day
Dose Level -3	Discontinue treatment

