7.2.2.1. Dose Modifications

Table 8: Dose Modification Criteria

Toxicity	Dose Modification and Discontinuation
Grade 4 neutropenia that occurs during the 21-day dosing period Grade 3 or 4 febrile neutropenia Grade 4 neutropenia of ≥ 5 days duration during the treatment rest period	
 • Interrupt pomalidomide until the neutrophil count recovers to ≥ 1000/mm³ and no fever (≤ 38.3 °C) (if applicable). • If the toxicity resolves and the subject meets eligibility parameters to resume as described in the protocol within 14 days (eg, ANC ≥ 1000/mm³; platelets ≥ 100,000/mm³), the subject should re-initiate treatment at one dose level lower. • If the dose modifying toxicity does not resolve to meet the parameters as described in the protocol within 14 days of treatment being held, pomalidomide should be permanently discontinued.
Grade 3 or 4 platelet count decreased that occurs during the 21 day dosing period	
 • Transfuse platelets to a post-transfusion plate target of ≥ 100,000/μL if platelet count is < 50,000/mm³. • Interrupt pomalidomide until the platelet count recovers to ≥ 100,000/mm³ unsupported (defined as no platelet transfusion within 7 days and recovery from nadir). • If the toxicity resolves and the subject meets eligibility parameters to resume as described in the protocol within 14 days (eg, ANC ≥ 1000/mm³; platelets > 100,000/mm³), the subject should re-initiate treatment at one dose level lower. • If the toxicity does not resolve to meet the eligibility parameters as described in the protocol within 14 days of treatment being held, pomalidomide should be permanently discontinued.

Table 8: Dose Modification Criteria (Continued)

Toxicity	Dose Modification and Discontinuation

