Appendix F: Pomalidomide Dosing

Table 12: Pomalidomide Capsule Dosing Tables

2.6 mg/m²/day (Starting Dose)		
Minimum BSA (m²)	Maximum BSA (m²)	Daily Pomalidomide Dose (mg)
0.55	0.66	1.5
0.67	0.86	2.0
0.87	1.05	2.5
1.06	1.25	3.0
1.26	1.44	3.5
1.45	1.63	4.0
1.64	1.82	4.5
1.83	2.01	5.0
2.02	2.21	5.5
2.22	2.40	6.0
2.41	2.50	6.5
1.9 mg/m²/day (Dose Level -1)		
Minimum BSA (m²)	Maximum BSA (m²)	Daily Pomalidomide Dose (mg)
0.55	0.66	1.0
0.67	0.92	1.5
0.93	1.18	2.0
1.19	1.44	2.5
1.45	1.71	3.0
1.72	1.97	3.5
1.98	2.23	4.0
2.24	2.49	4.5
2.50	2.50	5.0

Table 12: Pomalidomide Capsule Dosing Tables (Continued)

1.3 mg/m²/day (Dose Level -2)		
Minimum BSA (m²)	Maximum BSA (m²)	Daily Pomalidomide Dose (mg)
0.55	0.66	0.5
0.67	0.96	1.0
0.97	1.34	1.5
1.35	1.73	2.0
1.74	2.11	2.5
2.12	2.50	3.0

BSA = body surface area.

Table 13: Pomalidomide Dosing Table – Oral Suspension

For subjects receiving pomalidomide as an oral suspension, please refer to the Pomalyst Oral Suspension Preparation Administration and Handling Guide for additional guidance.

Calculated Dose (mg/day)	Actual Dose Administered (mg/day)	Volume Administered (mL)
0.50 to 0.69	0.6	0.3
0.70 to 0.89	0.8	0.4
0.90 to 1.09	1.0	0.5
1.10 to 1.29	1.2	0.6
1.30 to 1.49	1.4	0.7
1.50 to 1.69	1.6	0.8
1.70 to 1.89	1.8	0.9
1.90 to 2.09	2.0	1.0
2.10 to 2.29	2.2	1.1
2.30 to 2.49	2.4	1.2
2.50 to 2.69	2.6	1.3
2.70 to 2.89	2.8	1.4
2.90 to 3.09	3.0	1.5
3.10 to 3.29	3.2	1.6
3.30 to 3.49	3.4	1.7
3.50 to 3.69	3.6	1.8
3.70 to 3.89	3.8	1.9
3.90 to 4.09	4.0	2.0
4.10 to 4.29	4.2	2.1
4.30 to 4.49	4.4	2.2
4.50 to 4.69	4.6	2.3
4.70 to 4.89	4.8	2.4
4.90 to 5.09	5.0	2.5
5.10 to 5.29	5.2	2.6
5.30 to 5.49	5.4	2.7
5.50 to 5.69	5.6	2.8
5.70 to 5.89	5.8	2.9

Table 13: Pomalidomide Dosing Table – Oral Suspension (Continued)

Calculated Dose (mg/day)	Actual Dose Administered (mg/day)	Volume Administered (mL)
5.90 to 6.09	6.0	3.0
6.10 to 6.29	6.2	3.1 ^a
6.30 to 6.49	6.4	3.2 ^a
6.50-6.69	6.6	3.3 ^a

^a For administered volumes > 3.0 mL, the dose should be split. For example, a volume of 3.2 mL can be administered as two doses of 1.6 mL each. A dose of 3.3 can be administered as two doses of 1.6 mL and 1.7 mL each.

Celgene Signing Page

This is a representation of an electronic record that was signed electronically in Livelink.
This page is the manifestation of the electronic signature(s) used in compliance with
the organizations electronic signature policies and procedures.

UserName: PPD

Title: PPD

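### For capsule-treated children with BSA 0.58–0.67 m², the round-to-nearest-0.5-mg rule in Section 7.2 conflicts with Table 12 and turns one required toxicity dose reduction into no reduction; the protocol should say that Table 12 governs

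*Protocol*

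**What the plan says.** Section 7.2 of the protocol sets the dose from body surface area: "The starting dose of pomalidomide will be 2.6 mg/m²/day, based on the subject's actual BSA". For capsules, "the pomalidomide dose should be calculated and rounded up or down to the nearest 0.5 mg as the prescribed dose". No exception is given. Later in the same section the Appendix F table is described as provided "to facilitate dosing calculation for both capsules and oral suspension". Neither place says what to do when the rule and the table disagree.

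Table 7 sets three dose levels: 2.6, 1.9 and 1.3 mg/m²/day. Table 8 (Section 7.2.2.1) directs that after listed toxicities, once these have resolved, "the subject should re-initiate treatment at one dose level lower". Section 7.2.2 allows two reductions in total and then states: "Subjects who again experience dose modifying toxicity after 2 dose reductions will be taken off pomalidomide therapy".

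Table 12 in Appendix F gives capsule doses for BSA 0.55 to 2.50 m² at each level. The entries that matter here are:

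| Level | Dose at 0.55–0.66 m² | Next row up |
|---|---|---|
| Start, 2.6 mg/m² | 1.5 mg | 2.0 mg at 0.67–0.86 m² |
| Level -1, 1.9 mg/m² | 1.0 mg | 1.5 mg at 0.67–0.92 m² |
| Level -2, 1.3 mg/m² | 0.5 mg | 1.0 mg at 0.67–0.96 m² |

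**The concern.** Capsules come in steps of 0.5 mg, which is coarse for a small child. When two dose levels fall within the same rounding interval, rounding to the nearest step prescribes the same number of milligrams for both. Table 12 avoids this; the written rule does not. A site that calculates and rounds is following the protocol as worded, yet may not lower the dose when Table 8 requires it.

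Three things are at stake:

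- **Safety.** The child resumes the same daily dose after, for example, Grade 4 neutropenia.
- **Continued treatment.** The empty step still counts as one of the two permitted reductions, so the child can reach mandatory discontinuation after only one real one.
- **Overdose classification.** Section 7.2.3 defines an overdose as more than 10% above the protocol-specified dose. With two candidate specified doses, a compliant site can be classed as overdosing. At Level -2 for 0.58–0.66 m², 1.0 mg is 100% above 0.5 mg.

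**Working it through.** **Inputs.** Dose levels 2.6, 1.9 and 1.3 mg/m²/day (Table 7); the rounding rule (Section 7.2); printed capsule doses (Table 12).

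**Method.** For each BSA from 0.55 to 2.50 m² in steps of 0.01 (196 values) and each level (588 cells), compute level × BSA, round to the nearest 0.5 mg, and compare with Table 12. Exact ties are not counted as conflicts, because the rule permits rounding either way. They occur at 2.6 × 1.25 = 3.25 mg, 1.9 × 2.50 = 4.75 mg and 1.3 × 2.50 = 3.25 mg.

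**Step 1: reproduce Table 12.** With ties rounded up, rule and table agree in 575 of 588 cells. Of the other 13, two are ties (start at 1.25 m², Level -2 at 2.50 m²). The remaining 11 are true conflicts:

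| Level | BSA (m²) | Calculated dose (mg) | Rule (mg) | Table 12 (mg) |
|---|---|---|---|---|
| Start | 0.67 | 2.6 × 0.67 = 1.742 | 1.5 | 2.0 |
| Level -1 | 0.66 | 1.9 × 0.66 = 1.254 | 1.5 | 1.0 |
| Level -2 | 0.58 to 0.66 (nine values) | 1.3 × 0.58 = 0.754 up to 1.3 × 0.66 = 0.858 | 1.0 | 0.5 |

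**Step 2: doses at start / Level -1 / Level -2.**

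| BSA (m²) | Literal rule (mg) | Table 12 (mg) |
|---|---|---|
| 0.58–0.65 | 1.5 / 1.0 / 1.0 | 1.5 / 1.0 / 0.5 |
| 0.66 | 1.5 / 1.5 / 1.0 | 1.5 / 1.0 / 0.5 |
| 0.67 | 1.5 / 1.5 / 1.0 | 2.0 / 1.5 / 1.0 |

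Example at 0.60 m²: Level -1 is 1.9 × 0.60 = 1.14 mg, which rounds to 1.0 mg. Level -2 is 1.3 × 0.60 = 0.78 mg, which also rounds to 1.0 mg.

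Within 0.55–2.50 m², the rule repeats a dose at consecutive levels at these ten BSA values only, and Table 12 never does. The BSA values with a conflict and those with an empty step are the same set. With unrounded BSA, the empty step is the second reduction from 0.75/1.3 = 0.577 to 1.25/1.9 = 0.658 m², and the first from there to 1.75/2.6 = 0.673 m².

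**Step 3: size of the lost reduction.**

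- Second reduction, 0.58–0.65 m²: 0% under the rule; nominal 1.3/1.9 - 1 = -31.6%; Table 12 0.5/1.0 - 1 = -50%.
- First reduction, 0.66–0.67 m²: 0% under the rule; nominal 1.9/2.6 - 1 = -26.9%; Table 12 -33% at 0.66 (1.5 to 1.0 mg) and -25% at 0.67 (2.0 to 1.5 mg).

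**Step 4: distance from the nominal mg/m² dose.**

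| Entry | Table 12 | Rule |
|---|---|---|
| Level -2 at 0.58 m² | 0.5/0.58 = 0.86 mg/m² (-33.7%) | 1.0/0.58 = 1.72 mg/m² (+32.6%) |
| Level -2 at 0.66 m² | 0.5/0.66 = 0.76 mg/m² (-41.7%) | 1.0/0.66 = 1.52 mg/m² (+16.6%) |
| Start at 0.67 m² | 2.0/0.67 = 2.99 mg/m² (+14.8%) | 1.5/0.67 = 2.24 mg/m² (-13.9%) |

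The starting dose at 0.67 m² is close to its neighbour: at 0.68 m², rule and table both give 2.0 mg, or 2.0/0.68 = 2.94 mg/m² (+13.1%).

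**The case against.** The strongest reply is that the protocol already prints the safe answer. Table 12 has a separate block for each level, every step goes down, and Section 7.2 points sites to it. Harm needs a site to calculate by hand and not notice that an unchanged dose contradicts Table 8. The interactive response system is used on Day 1 of each cycle, and if it or the pharmacy materials encode Table 12, the conflict never operates. The documents do not settle that.

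Reach is also narrow. A BSA near 0.60 m² corresponds by the Section 6.4.2.4 formula to, for illustration, a child of 14 kg and 96 cm. Many such children may receive the suspension, and Table 13 separates all three levels in this band (1.6/1.2/0.8 mg at 0.58–0.65 m², 1.8/1.2/0.8 mg at 0.66–0.67 m²). The child must be on capsules, have a dose-modifying toxicity (a second one at 0.58–0.65 m²) and be dosed by calculation.

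The repeated dose is also below the nominal level at which toxicity occurred: 1.54–1.72 mg/m² against 1.9 at 0.58–0.65 m², and 2.24–2.27 against 2.6 at 0.66–0.67 m². Three of the 11 conflicts lie within 0.004–0.008 mg of a rounding midpoint, so carrying a third BSA decimal could flip them. Finally, at Level -2 the rule is nearer to nominal than the table towards the top of the band.

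The points on reach stand, and they keep this a modest matter. They do not remove the conflict: the rule is what sets the prescribed dose, and the table is described only as an aid. A dose below nominal is still the dose on which that child had the toxicity. The other eight conflicts are not near-ties. Closeness to nominal is secondary when the purpose of the step is to lower the dose.

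**Conclusion.** The concern holds. Section 7.2 and Table 12 conflict in 11 entries at BSA 0.58–0.67 m². Applied literally, the rule removes exactly one of the two dose reductions at each of those ten values: the second at 0.58–0.65 m², the first at 0.66–0.67 m². The defect is the unqualified rule, not the table. The exact match between the conflicts and the empty steps suggests that the table was built to keep the levels distinct, but the documents do not say so.

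This rests on capsule dosing, BSA unchanged between the two levels and recorded to two decimals, and a site that rounds instead of reading the table. How many children would meet these conditions cannot be estimated from the documents. No endpoint, analysis population or decision rule is affected. It should be fixed because the consequence is direct for a small child with toxicity and the correction costs almost nothing.

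**What to change.** Add one sentence to Section 7.2: where Table 12 differs from rounding to the nearest 0.5 mg (BSA 0.58–0.67 m²), the Table 12 capsule dose applies, so that each dose level is a lower mg dose than the one before. Send a site memo, and check that the response system and pharmacy instructions use Table 12.

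The clinical team should confirm the 2.0 mg starting dose at 0.67 m² (+14.8% on a starting dose that is itself the MTD). If they prefer 1.5 mg there, 0.67 m² should move to the 0.55–0.66 m² row at all three levels; changing the starting dose alone would recreate 1.5 to 1.5 mg. Do not shift the Table 12 cut-offs to match literal rounding, which would lose a reduction at all ten BSA values.

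The sentence does not help below 0.55 m², where Table 12 has no rows and rounding also loses the first reduction (1.0 to 1.0 mg at 0.40–0.48 m²). The team may wish to cover that range in the same edit.

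Cost: one sentence and a memo. Table 12 is unchanged unless the 0.67 m² dose is revised.
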